12.2.1.2 Secondary analysis

The change from baseline to Week 12 in FPG will be analysed based on the similar ANCOVA model as in the primary efficacy analysis for HbA1c.

The proportion of subjects achieving a therapeutic glycemic response defined as HbA1c < 7.0% at Week 12 will be summarized by treatment groups. The 2-sided 95% confidence intervals for the response rate within each treatment group as well as for the difference in response rate between each of dapagliflozin treatment group and the placebo treatment group will be estimated. The proportions will be compared between each of dapagliflozin treatment groups versus placebo using a two-sided Fisher's exact test.

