Inclusion criteria for Randomization

8. No clinically significant abnormalities in any pre-randomization laboratory value, electrocardiogram (ECG), vital sign or physical examination, which in the Investigator's opinion, would preclude randomisation
9. Subject must demonstrate good compliance with study medication (\geq 80% and \leq 120%) during Period B
10. Subjects having inadequate glycemic control on diet and exercise alone, defined as HbA1c \geq 7.0% and \leq 10% at 1 week before randomization (Visit 5)

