11. EVALUATION AND CALCULATION OF VARIABLES BY ASTRAZENECA

11.1 Calculation or derivation of efficacy variable(s)

Baseline is defined as the assessment performed at pre-dose on Week 0.

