12.1.1.1 Full analysis set

The full analysis set will include all randomised patients who received at least one dose of study medication, and who have a non-missing baseline value and at least one post-baseline efficacy value for at least one efficacy variable. The patients will be analysed according to the treatment group to which they were randomised, regardless of the actually treatment taken.

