12.2.1.1 Primary analysis

For the primary efficacy analysis, the change from baseline in HbA1c at Week 12 will be analysed based on an analysis of covariance (ANCOVA) model including treatment group as a fixed effects and baseline as a covariate. Based on the ANCOVA model, the point estimates and 2-sided 95% confidence intervals for the mean changes within each treatment group as well as for the differences in mean changes between each of dapagliflozin treatment group and the placebo treatment group will be calculated. Pair-wise comparisons of dapagliflozin treatment groups vs. placebo group will be made with multiplicity of tests adjusted by Dunnett's method at overall 2-sided significance level 0.05.

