12.3 Determination of sample size

The sample size for this study is calculated based upon the results observed in a similarly designed study for dapagliflozin (MB102008). From that study, the mean value and SD for the HbA1c change from baseline was -0.54% and 0.74%, respectively, as estimated from the the placebo-corrected change in the 5 mg group. The sample size calculation based on these results is considered appropriate, even though a smaller reduction in HbA1c could also be considered clinically meaningful. Then with 53 subjects per treatment group in the full analysis set, there is 90% power to detect a difference in mean change from baseline of 0.54% for HbA1c between any given dapagliflozin group and placebo using a 2-sample t-test at the overall 2-sided significance of 0.05, adjusted for multiplicity (4 tests against placebo) by Dunnett's method. Assuming a similar proportion (4%) of randomised patients are excluded from the full analysis set as seen in Study MB102008, 55 subjects per treatment group are needed to be randomised.

The sample size for this study was selected to be consistent with the research hypothesis as described in Section 1.2.

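### The Week 12 responder endpoint is compared by an unadjusted Fisher's exact test that ignores Week 0 HbA1c, at a cost of roughly 16 to 20 points of power

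*Protocol*

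**What the plan says.** Section 2.2 names two secondary outcomes: change in FPG and the proportion of subjects below 7% HbA1c. Section 12.2.1.2 analyses FPG with an ANCOVA like the primary one. For the second outcome, a "therapeutic glycemic response defined as HbA1c < 7.0% at Week 12", it plans 95% confidence intervals for the rates and their differences and then states: "The proportions will be compared between each of dapagliflozin treatment groups versus placebo using a two-sided Fisher's exact test". It names no covariate.

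The primary model in Section 12.2.1.1 is an ANCOVA "including treatment group as a fixed effects and baseline as a covariate". Section 11.1 says: "Baseline is defined as the assessment performed at pre-dose on Week 0".

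The entry threshold is read at another visit. Randomisation criterion 10 in Section 4.1 admits "Subjects having inadequate glycemic control on diet and exercise alone, defined as HbA1c" from 7.0% to 10%, measured at Visit 5, one week before randomisation. The full analysis set (Section 12.1.1.1) takes randomised, dosed patients "who have a non-missing baseline value and at least one post-baseline efficacy value for at least one efficacy variable" and sets no lower limit on Week 0 HbA1c.

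Section 12.3 sizes the trial for the primary endpoint only: "the mean value and SD for the HbA1c change from baseline was -0.54% and 0.74%, respectively", with 53 per group for 90% power. It claims no power for the responder comparison.

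**The concern.** Whether a subject entering at 7–10% ends below 7.0% depends heavily on where that subject starts. The protocol adjusts for the starting value in HbA1c change and in FPG, but not in the endpoint that dichotomises HbA1c. Two things follow. The comparison has less power than data already collected could give, and any chance difference in baseline HbA1c between arms of about 53 passes straight into the unadjusted response difference. Fisher's test adds a second loss, because at these response rates its actual size is well below the nominal 5%. The protocol states this choice outright, so it is not a detail left open for the SAP.

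**Working it through.** **1. The protocol's own figure.** The inputs from Section 12.3 are a difference of 0.54, SD 0.74, n = 53 per group and Dunnett with 4 comparisons. The noncentrality is 0.54 / (0.74 × √(2/53)) = 0.54 / 0.1438 = 3.76. The two-sided Dunnett critical value (4 comparisons, 260 df) is 2.457. Noncentral t power is 0.902, so the stated 90% reproduces.

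**2. How much baseline matters.** Assume zero mean change on placebo and SD 0.74 around the Week 0 value B. Then P(response) = Φ((7.0 − B + 0.54·active) / 0.74).

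- B = 7.5: placebo Φ(−0.68) = 0.25; active Φ(0.05) = 0.52.
- B = 8.3: placebo Φ(−1.76) = 0.04; active Φ(−1.03) = 0.15.

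A 0.8-point difference in starting value moves the placebo response chance from about 25% to 4%. In the simulations below the correlation of baseline with response is about −0.4.

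**3. Power by simulation.** One dose against placebo, 53 per arm, two-sided nominal 0.05 per comparison. Week −1 HbA1c is screened to 7–10%, Week 0 is the baseline, and Week 12 = Week 0 − 0.54·active + N(0, 0.74²). The pre-screening mean, between-subject SD and visit-to-visit SD are assumptions; the protocol gives none of them. There were 4,000 replicates per row.

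| Mean / SD / visit SD | Fisher | Uncorrected chi-square | Adjusted logistic (Wald) | Size: Fisher / Wald |
|---|---|---|---|---|
| 8.0 / 0.8 / 0.2 | 0.423 | 0.509 | 0.587 | 0.024 / 0.042 |
| 7.5 / 0.7 / 0.2 | 0.558 | 0.643 | 0.728 | 0.033 / 0.050 |
| 7.5 / 0.7 / 0.3 | 0.531 | 0.622 | 0.726 | 0.029 / 0.048 |
| 8.3 / 0.9 / 0.2 | 0.326 | 0.420 | 0.492 | 0.019 / 0.026 |

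The total gain, Wald minus Fisher, is 16.4, 17.0, 19.5 and 16.6 points. It splits as follows:

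- Fisher to chi-square (conservatism): 8.6, 8.5, 9.1 and 9.4 points.
- Chi-square to adjusted model (covariate): 7.8, 8.5, 10.4 and 7.2 points.

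With visit-to-visit SD 0.1 and mean 7.5, Fisher reaches 0.579, the top of its range. Repeat simulations over much the same range gave 33–51% for Fisher and 48–71% for the adjusted Wald test, with null rejection of 1.5–3.4% and 2.4–5.8%.

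**4. Sensitivity.** Here the adjusted test is a likelihood-ratio test, which is slightly liberal. Letting change depend on baseline with slope −0.2 or −0.4 gives Fisher 0.437 and 0.476 against 0.634 and 0.647. Shifting the placebo change by +0.2 or −0.2 gives 0.334 and 0.462 against 0.544 and 0.682. The direction did not change in any scenario.

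**5. Subjects below 7.0% at Week 0.** About 2–10% of simulated subjects fall here, and they make up 9–23% of responders in the four rows above. Dropping them has these effects on power:

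- Fisher: 0.423 to 0.440, 0.558 to 0.576, 0.531 to 0.541, 0.326 to 0.354.
- Adjusted Wald: 0.587 to 0.564, 0.728 to 0.685, 0.726 to 0.668, 0.492 to 0.469.

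**The case against.** Fisher's test controls type I error, the protocol promises no power for this endpoint, confidence intervals are planned alongside the p-value, and HbA1c itself is analysed with baseline adjustment as the primary endpoint. All of that stands. It limits the point to efficiency but gives no reason to leave out a measured predictor that the same section uses for FPG.

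A second objection is that Fisher and the adjusted model are not compared at the same actual size. With the adjusted Wald test matched to Fisher's actual size, power is 0.53 against 0.43, 0.60 against 0.50, 0.61 against 0.49 and 0.40 against 0.33, a gain of 7 to 12 points. This also stands as a matter of attribution: a reader might credit the whole 16–20 points to baseline, and only about half belongs there. The other half is still recoverable, because the Wald test at nominal 5% stays at or below 5% in the four tabulated scenarios.

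A third objection is that the figures rest on baseline inputs the protocol does not give. That is correct for the magnitude.

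A stronger reading is also tempting. Eligibility is read at Visit 5 and baseline at Week 0, so some subjects may be below 7.0% before the first dose, and a reader might infer that counting them biases the comparison or drains its power. The documents do not support this. The endpoint is the proportion attaining a level, not a change. Such a subject must still be below 7.0% at Week 12, or at the last earlier post-baseline value under the LOCF rule of Section 12.2.1. Week 0 status precedes dosing and is balanced in expectation by randomisation. Excluding these subjects gains Fisher 1 to 3 points, costs the adjusted model 2 to 6 points, and departs from the full analysis set.

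**Conclusion.** The point holds as an efficiency weakness in one secondary endpoint. Under the protocol's own effect, SD and group size, and over the assumed baselines (pre-screening mean 7.5–8.3%, SD 0.7–0.9, visit-to-visit SD 0.1–0.3), Fisher has roughly 33–58% power. A baseline-adjusted logistic model has about 48–73%. In the four tabulated scenarios Fisher gives up about a quarter to a third of the attainable power (for example 1 − 0.423/0.587 = 28%). Its actual size is about 1.5–3.5%.

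Confidence is high in the direction and moderate in the size. Nothing here makes the planned test invalid, and the primary analysis and its sample size are untouched. The Visit 5 / Week 0 gap, with an assumed 1–10% of subjects below 7.0% at Week 0, bears on what response means and is not a source of bias or of material power loss.

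**What to change.** Before unblinding, change Section 12.2.1.2, or record the change in the SAP. On the full analysis set, compare each dose with placebo by logistic regression with treatment and Week 0 HbA1c, using a Wald or Firth-type test. Report the covariate-standardised risk difference with its 95% CI, and keep Fisher's exact test as a sensitivity analysis. Do not restrict the main analysis to Week 0 HbA1c of 7.0% or more; at most, report that restriction as supplementary.

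No new data are needed. The costs are a modelling assumption about the form of the baseline effect and a slight small-sample deviation in size (simulated at about 2–6%). An ordinary likelihood-ratio or score test is a little liberal here (likelihood-ratio size 5.6–6.6% in the four scenarios), hence the preference for Wald or Firth.

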12.2.1.3 Tertiary analysis

The change from baseline to Week 12 in 180 minutes AUC on postprandial glucose, insulin and C-peptide response to OGTT, fasting plasma insulin, fasting plasma C-peptide, beta-cell function (using HOMA2), and insulin resistance index (using HOMA2) will be analysed based on the similar ANCOVA model as in the primary efficacy analysis for HbA1c.

At each time point, the observed value and changes from baseline for all continuous efficacy variables will be summarised using descriptive statistics. For categorical efficacy variables, the number of subjects in each category will be summarised at each time point.

12.2.2 Analysis of safety data

All safety data will be listed and summarised descriptively by treatment group.

The number and percentage of subjects who had any AEs, SAEs, AEs that lead to discontinuation, drug-related AEs and other significant AEs will be summarised.

Adverse events will be classified by body system and by preferred term using MedDRA. The number and percentage of subjects with AEs occurring after the first dosing date (including the first dosing date) by body system and by preferred term will be summarised. If necessary, similar summary will be made for SAEs and drug-related AEs.

For continuous safety variables, observed value and changes from baseline at each time point will be summarised using descriptive statistics. For categorical safety variables, the number of subjects in each category will be summarised at each time point.

All laboratory safety variables outside the reference range will be listed.

12.2.3 Analysis of PK data

The PK properties of dapagliflozin will be evaluated by population PK methodology and reported as necessary in a separate PK report, including estimates of population mean PK parameters, between-patient variability as well as predictions of individual PK parameters and exposures measures (ie, apparent clearance [CL/F], apparent volume of distribution [Vd/F] and exposure measures (ie, AUC, C_{min}). Possible covariate effects on PK parameters (e.g. renal function on CL/F) may be identified and quantified. A detailed population PK analysis plan will be prepared prior to data base lock.

12.3 Determination of sample size

The sample size for this study is calculated based upon the results observed in a similarly designed study for dapagliflozin (MB102008). From that study, the mean value and SD for the HbA1c change from baseline was -0.54% and 0.74%, respectively, as estimated from the the placebo-corrected change in the 5 mg group. The sample size calculation based on these results is considered appropriate, even though a smaller reduction in HbA1c could also be considered clinically meaningful. Then with 53 subjects per treatment group in the full analysis set, there is 90% power to detect a difference in mean change from baseline of 0.54% for HbA1c between any given dapagliflozin group and placebo using a 2-sample t-test at the overall 2-sided significance of 0.05, adjusted for multiplicity (4 tests against placebo) by Dunnett's method. Assuming a similar proportion (4%) of randomised patients are excluded from the full analysis set as seen in Study MB102008, 55 subjects per treatment group are needed to be randomised.

The sample size for this study was selected to be consistent with the research hypothesis as described in Section 1.2.

12.4 Data monitoring committee – Not Applicable

13. IMPORTANT MEDICAL PROCEDURES TO BE FOLLOWED BY THE INVESTIGATOR

13.1 Medical emergencies and AstraZeneca contacts

The Principal Investigator is responsible for ensuring that procedures and expertise are available to handle medical emergencies during the study. **A medical emergency usually constitutes an SAE and is to be reported as such, see Section 6.4.4**

In the case of a medical emergency the investigator may contact the Monitors or the Study Delivery Team Leader. If the Study Delivery Team Leader is not available, contact the *Study Delivery Team Physician*/other physician at the AstraZeneca Research and development.

Name	Role in the study	Address & telephone number

13.2 Overdose

Overdose is defined as the accidental or intentional ingestion of any dose of a product that is considered both excessive and medically important. Once an investigator decides that a particular occurrence is an overdose, it must be reported using the SAE module of eCRF (see Section 6.4.4).

13.3 Pregnancy

All outcomes of pregnancy should be reported to AstraZeneca.

13.3.1 Maternal exposure

If a subject becomes pregnant during the course of the study investigational product should be discontinued immediately.

Pregnancy itself is not regarded as an adverse event unless there is a suspicion that the investigational product under study may have interfered with the effectiveness of a contraceptive medication. Congenital abnormalities/birth defects and spontaneous miscarriages should be reported and handled as SAEs. Elective abortions without complications should not be handled as AEs. The outcome of all pregnancies (spontaneous miscarriage, elective termination, ectopic pregnancy, normal birth or congenital abnormality) should be followed up and documented even if the subject was discontinued from the study.

If any pregnancy occurs in the course of the study, then investigators or other site personnel inform appropriate AstraZeneca representatives **within one day** ie, immediately but no later than the **end of the next business day** of when he or she becomes aware of it.

The designated AstraZeneca representative works with the investigator to ensure that all relevant information is provided to the AstraZeneca Patient Safety data entry site within 1 or 5 days for SAEs, see Section 6.4.4 and within 30 days for all other pregnancies

The same timelines apply when outcome information is available.

The PREGREP module in the CRF is used to report the pregnancy and the PREGOUT is used to report the outcome of the pregnancy.

Appendix B
Additional Safety Information

FURTHER GUIDANCE ON THE DEFINITION OF A SERIOUS ADVERSE EVENT (SAE)

Life threatening

‘Life-threatening’ means that the subject was at immediate risk of death from the AE as it occurred or it is suspected that use or continued use of the product would result in the subject’s death. ‘Life-threatening’ does not mean that had an AE occurred in a more severe form it might have caused death (eg, hepatitis that resolved without hepatic failure).

Hospitalisation

Outpatient treatment in an emergency room is not in itself a serious AE, although the reasons for it may be (eg, bronchospasm, laryngeal oedema). Hospital admissions and/or surgical operations planned before or during a study are not considered AEs if the illness or disease existed before the subject was enrolled in the study, provided that it did not deteriorate in an unexpected way during the study.

Important medical event or medical intervention

Medical and scientific judgement should be exercised in deciding whether a case is serious in situations where important medical events may not be immediately life threatening or result in death, hospitalisation, disability or incapacity but may jeopardize the subject or may require medical intervention to prevent one or more outcomes listed in the definition of serious. These should usually be considered as serious.

Simply stopping the suspect drug does not mean that it is an important medical event; medical judgement must be used.

Examples of such events are:

- Angioedema not severe enough to require intubation but requiring iv hydrocortisone treatment
- Hepatotoxicity caused by paracetamol (acetaminophen) overdose requiring treatment with N-acetylcysteine
- Intensive treatment in an emergency room or at home for allergic bronchospasm
- Blood dyscrasias (eg, neutropenia or anaemia requiring blood transfusion, etc) or convulsions that do not result in hospitalisation
- Development of drug dependency or drug abuse.

A GUIDE TO INTERPRETING THE CAUSALITY QUESTION

The following factors should be considered when deciding if there is a “reasonable possibility” that an AE may have been caused by the drug.

- Time Course. Exposure to suspect drug. Has the subject actually received the suspect drug? Did the AE occur in a reasonable temporal relationship to the administration of the suspect drug?
- Consistency with known drug profile. Was the AE consistent with the previous knowledge of the suspect drug (pharmacology and toxicology) or drugs of the same pharmacological class? OR could the AE be anticipated from its pharmacological properties?
- Dechallenge experience. Did the AE resolve or improve on stopping or reducing the dose of the suspect drug?
- No alternative cause. The AE cannot be reasonably explained by another aetiology such as the underlying disease, other drugs, other host or environmental factors.
- Rechallenge experience. Did the AE reoccur if the suspected drug was reintroduced after having been stopped? AstraZeneca would not normally recommend or support a rechallenge.
- Laboratory tests. A specific laboratory investigation (if performed) has confirmed the relationship?

A “reasonable possibility” could be considered to exist for an AE where one or more of these factors exist.

In contrast, there would not be a “reasonable possibility” of causality if none of the above criteria apply or where there is evidence of exposure and a reasonable time course but any dechallenge (if performed) is negative or ambiguous or there is another more likely cause of the AE.

In difficult cases, other factors could be considered such as:

- Is this a recognised feature of overdose of the drug?
- Is there a known mechanism?

Ambiguous cases should be considered as being a “reasonable possibility” of a causal relationship unless further evidence becomes available to refute this. Causal relationship in cases where the disease under study has deteriorated due to lack of effect should be classified as no reasonable possibility.

Bristol-Myers Squibb

Clinical Study Protocol Appendix C

Drug Substance	Dapagliflozin
Study Code	D1692C00005
Edition Number	1
Date	

Appendix C
International Airline Transportation Association (IATA) 6.2 Guidance Document

LABELLING AND SHIPMENT OF BIOHAZARD SAMPLES

International Airline Transportation Association (IATA) classifies biohazardous agents into 3 categories (http://www.iata.org/whatwedo/cargo/dangerous_goods/infectious_substances.htm). For transport purposes the classification of infectious substances according to risk groups was removed from the Dangerous Goods Regulations (DGR) in the 46th edition (2005). Infectious substances are now classified either as Category A, Category B or Exempt. There is no direct relationship between Risk Groups and categories A and B.

Category A Infectious Substances are infectious substances in a form that, when exposure to it occurs, is capable of causing permanent disability, life-threatening or fatal disease in otherwise healthy humans or animals. Category A pathogens are eg, Ebola, Lassa fever virus:

- are to be packed and shipped in accordance with IATA Instruction 602.

Category B Infectious Substances are infectious Substances that do not meet the criteria for inclusion in Category A. Category B pathogens are eg, Hepatitis A, B, C, D, and E viruses, Human immunodeficiency virus (HIV) types 1 and 2. They are assigned the following UN number and proper shipping name:

- UN 3373 – Biological Substance, Category B
- are to be packed in accordance with UN3373 and IATA 650

Exempt - all other materials with minimal risk of containing pathogens

- Clinical trial samples will fall into Category B or exempt under IATA regulations
- Clinical trial samples will routinely be packed and transported at ambient temperature in IATA 650 compliant packaging (http://www.iata.org/whatwedo/cargo/dangerous_goods/infectious_substances.htm)
- **Biological samples transported in dry ice require additional dangerous goods specification for the dry-ice content**
- IATA compliant courier and packaging materials should be used for packing and transportation and packing should be done by an IATA certified person, as applicable

- Samples routinely transported by road or rail are subject to local regulations which require that they are also packed and transported in a safe and appropriate way to contain any risk of infection or contamination by using approved couriers and packaging / containment materials at all times. The IATA 650 biological sample containment standards are encouraged wherever possible when road or rail transport is used.

Bristol-Myers Squibb

